5.2 Efficacy Endpoint-related Definitions

Best Overall Response (BOR)

The subject's best response assignment depends on the findings of both target and non-target disease and also takes into consideration the appearance of new lesions and confirmation of response based on the findings from MRI/CT scans. Confirmation of progressive disease is not required. BOR is based on all post-baseline disease assessments that occur prior to the initiation of subsequent anticancer treatment. At least 5 weeks from the first dose of IP must elapse without radiological disease progression to meet the minimum criteria for SD duration in order to assign a BOR of SD. In general, subjects not classifiable under the RECIST 1.1 response categories due to inadequate data or early death are classified as not evaluable (NE) for BOR but will be counted in the denominator of all response rate calculations. BOR per RECIST 1.1 has the following possible categories: complete response (CR), partial response (PR), stable disease (SD), progressive disease (PD), not evaluable (NE). The rules for deriving the BOR are detailed in Appendix B.

Objective Response (OR)

OR is defined as a BOR of CR or PR per RECIST 1.1. Subject without a post-baseline tumor assessment is considered non-responder.

Objective Response Rate (ORR)

ORR is defined as proportion of subjects with BOR of CR or PR per RECIST 1.1.

Disease Control (DC)

DC is defined as a BOR of CR or PR or SD per RECIST 1.1.

Disease Control Rate (DCR)

DCR is defined as proportion of subjects with a BOR of CR or PR or SD per RECIST 1.1.

Duration of Disease Control (DoDC)

DoDC is defined as time from **the date of first dose of tarlatamab** until the first documentation of disease progression or death due to any cause, whichever occurs first. Only subjects with a BOR of confirmed response (CR/PR) or SD are evaluated for DoDC.

DoDC (Months) = (earlier of progressive disease date or death date – **date of first dose of tarlatamab** + 1) × 12 / 365.25

DoDC is censored following the same censoring rules as PFS ([Appendix C](#)).

Duration of Response (DOR)

DOR is defined as time from first documentation of CR or PR per RECIST 1.1 until the first documentation of progressive disease or death due to any cause, whichever occurs first. Only subjects who with a BOR of confirmed response (CR/PR) are evaluated for DOR.

DOR (Months) = (earlier of progressive disease date or death date – response start date + 1) × 12 / 365.25

DOR is censored following the same rules as PFS ([Appendix C](#)).

Progression-free survival (PFS)

PFS is defined as time from **the date of first dose of tarlatamab** to the earlier of progressive disease per RECIST 1.1 or death due to any cause, whichever occurs first.

PFS (Months) = (earlier of progressive disease date or death date – **date of first dose of tarlatamab** + 1) × 12 / 365.25

[Appendix C](#) details the censoring rules for PFS.

Overall Survival (OS)

OS is defined as time from **the date first dose of tarlatamab** until event of death due to any cause. Subjects still alive are censored at the date last known to be alive. If the date

last known to be alive is after the date that triggers the analysis (i.e., the data cut-off date), the subject is censored at the data cut-off date.

OS (Months) = (death date – **date of first dose of tarlatamab** + 1) × 12 / 365.25

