treatments must be withheld, and the investigator or designee should notify the sponsor's medical monitor as soon as possible. A subject may be allowed to resume study drugs if both the investigator and sponsor's medical monitor agree to restart study therapy.

6.1.7 Continuation on Investigational Product Treatment After First Radiologic Disease Progression

This section details the conditions necessary to allow continued study treatment after first disease progression in subjects that, in the investigator's judgment, continue to have clinical benefit. All of the following criteria must be met:

- Subject continues to have clinical benefit per the investigator's judgment.
- Subject has stable ECOG PS.
- Absence of threat to vital organs or critical anatomical sites (eg, respiratory failure due to tumor compression, spinal cord compression) requiring urgent alternative medical intervention with persistent immediate threat to vital organs after intervention. The presence of brain metastases is allowed provided the lesions are amenable to radiation therapy or dexamethasone (or corticosteroid equivalent), and the subject is clinically stable in the investigator's judgment.
- Subject continues to tolerate study drug.
- No other treatment discontinuation criteria are met ([Table 6-2](#) and **Section 11.7.1**).
- No significant, unacceptable, or irreversible toxicities related to any dose of the study treatment or treatment-related adverse events of Common Terminology Criteria for Adverse Events (CTCAE) grade 3 at the current dose at the time of progression.
- Radiation therapy is permitted after discussion with the medical monitor. Palliative radiation and/or surgery for new, progressive, or symptomatic lesions is permitted. Study treatment must be held during either treatment (radiation and/or surgery) and the treatment must be completed at least 7 days before the subsequent dose of study treatment.

Subjects should continue to perform all protocol-required procedures as noted in the Schedule of Activities (Section [1.3](#); imaging, labs, and clinic visits).

Any subsequent (investigator determined) progressive disease per RECIST 1.1 from a new baseline set at initial progression will result in permanent discontinuation of study treatment.

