11.10.5 Evaluation of Best Overall Response

The subject's best response assignment will depend on the findings of both target and non-target disease and will also take into consideration the appearance of new lesions and confirmation of response. Best overall response (BOR) will be based on all post-baseline disease assessments that occur prior to the initiation of subsequent

anticancer treatment. At least 5 weeks from the first dose of tarlatamab must elapse without radiological disease progression to meet the minimum criteria for SD duration in order to assign a BOR of SD. In general, subjects not classifiable under the RECIST 1.1 response categories due to inadequate data or early death will be classified as non-evaluable (NE) for BOR but will be counted in the denominator of all response rate calculations.

Table 11-5. Time Point Overall Response

Target Lesions	Non-target Lesions	New Lesions	Overall Response
Subjects with Target (± Non-target) Disease			
CR	CR or NA	No	CR
CR	Non-CR/non-PD or NE	No	PR
PR	CR or Non-CR/Non-PD or NE or NA	No	PR
SD	CR or Non-CR/Non-PD or NE or NA	No	SD
PD	Any	Any	PD
Any	PD	Any	PD
Any	Any	Yes	PD
NE	CR or Non-CR/Non-PD or NE or NA	No	NE
Subjects with Non-target Disease Only			
NA	CR	No	CR
NA	Non-CR/Non-PD	No	(Non-CR/Non-PD) ^a
NA	CR or Non-CR/Non-PD	NE	(Non-CR/Non-PD) ^a
NA	PD	Any	PD
NA	Any	Yes	PD
NA	NE	No	NE

CR = complete response; NA = Not applicable; NE = Not evaluable; PD = progressive disease; PR = partial response; RECIST = Response Evaluation Criteria in Solid Tumors; SD = stable disease.

^a Per RECIST 1.1, "SD (Non-CR/Non-PD)" is preferred over "SD" for Non-Target disease since SD is increasingly used as endpoint for assessment of efficacy in some trials so to assign this category when no lesions can be measured is not advised.

Table 11-6. Best Overall Response When Confirmation of Complete Response (CR) and Partial Response (PR) Required

Overall Response First Time Point	Overall Response Second Time Point	Best Overall Response
CR	CR	CR
CR	PR	SD, PD or PR ^a
CR	SD	SD provided minimum criteria for SD duration met, otherwise, PD
CR	PD	SD provided minimum criteria for SD duration met, otherwise, PD
CR	NE	SD provided minimum criteria for SD duration met, otherwise, NE
PR	CR	PR
PR	PR	PR
PR	SD	SD
PR	PD	SD provided minimum criteria for SD duration met, otherwise, PD
PR	NE	SD provided minimum criteria for SD duration met, otherwise, NE
NE	NE	NE

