ORR by BICR per RECIST 1.1 in Chinese subjects with advanced SCLC who have progressed on or recurred following 1 platinum-based regimen as 1L therapy (including a PD-1/ PD-[L]1) and at least 1 other prior line of therapy (re-treatment with a platinum based regimen is considered a second-line of therapy) prior to start of new cancer therapy (while-on-treatment strategy).

Estimand(s) for Key Secondary Objective(s)

Not applicable.

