Appendix B. BOR per RECIST 1.1

BOR by investigator will be derived based on the timepoint response collected in the RECIST 1.1 CRF. BOR by central review will be derived from timepoint response shared by the central imaging vendor. At each time point, BOR will be derived based upon the evaluated timepoints up to and including the current MRI/CT assessment. The following rules will apply to BOR:

- CR is better than PR is better than SD is better than PD is better than NE
- For a BOR of SD, a duration of ≥ 35 days since the cycle 1 day 1 is required
- For a BOR of CR or PR confirmation is required. PR can be confirmed by a PR or CR. The confirmation assessment must be in a consecutive assessment ≥ 28 days after the initially observed assessment of CR or PR except the following cases:
 - An unlimited number of intermittent assessments of NE or CR <28 days can occur between the initial response and the confirmation of CR. For example, BL, CR, NE, NE, NE, CR – the CR at post-baseline 1 is confirmed at post-baseline 5. SD is not allowed between CR and subsequent confirmation CR.
 - An unlimited number of intermittent assessments of NE, SD, PR or CR <28 days can occur between the initial response and the confirmation of PR. For example, BL, PR, SD, SD, SD, PR – the PR at post-baseline 1 is confirmed at post-baseline 5.

[Table 14-2](#) provides the BOR determination per RECIST 1.1 where confirmation of response (CR/PR) is required. [Table 14-3](#) outlines the steps to derive Confirmed_BOR (step 1) given timepoint assessments.

At interim analyses (if any), due to lack of sufficient follow-up time for confirmation scan, study team may choose to report both confirmed responders and unconfirmed responders (subjects had an initial PR or CR and still has potential for future confirmative scans). Interim_BOR is defined to include unconfirmed responders in addition to those who achieve Confirmed_BOR. [Table 14-3](#) step 2 provides details to derive the unconfirmed responders.

Table 14-2. BOR per RECIST 1.1 where Confirmation of CR/PR is Required

Criterion	Timepoint T1 Response	T1 ≥ 35 days after C1D1?	Timepoint T2 Response	T2 ≥ 35 days after C1D1?	T2 ≥ 28 days after T1?	BOR_temp
C1	CR	Yes	CR	-	Yes	CR
C2			CR	-	No	SD
C3			PR, SD	-	-	Query data*

C4			PD	-	-	SD
C5			NE, No further evaluations			SD
C6		No	CR	-	Yes	CR
C7			CR	Yes	No	SD
C8			CR	No	No	NE
C9			PR, SD	-	-	Query data*
C10			PD	-	-	PD
C11			NE, No further evaluations			NE
C12	PR	Yes	CR, PR	-	Yes	PR

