C13			CR, PR	-	No	SD
C14			SD	-	-	SD
C15			PD	-	-	SD
C16			NE, No further evaluations			SD
C17		No	CR, PR	-	Yes	PR
C18			CR, PR	Yes	No	SD
C19			CR, PR	No	No	NE
C20			SD	Yes	-	SD
C21			SD	No		NE
C22			PD	-	-	PD
C23			NE, No further evaluations			NE
C24	SD	Yes	CR, PR, SD, PD, NE, no more evaluation			SD
C25		No	CR, PR, SD	Yes	-	SD
C26			CR, PR, SD	No	-	NE
C27			PD	-	-	PD
C28			NE, No further evaluations			NE
C29	PD		-			PD
C30	NE	-	NE, No further evaluations			NE
C31		-	CR, PR, SD	Yes	-	SD
C32		-	CR, PR, SD	No	-	NE
C33		-	PD	-	-	PD

*If a CR is truly met at first time point, then any disease seen at a subsequent time point, even disease meeting PR criteria relative to baseline, makes the disease PD at that point (since disease must have reappeared after CR). Best response would depend on whether minimum duration for SD was met. However, sometimes 'CR' may be claimed when subsequent scans suggest small lesions were likely still present and in fact the patient had PR, not CR at the first time point. Under these circumstances, the original CR should be changed to PR. A CR may also be followed by a PR when the target lesion assessment is CR and the non-target lesion assessment is NE. In both of these situations, the best response is PR.

Table 14-3. BOR Derivation Step

Step 1. Derive Confirmed_BOR at each visit

Derive Confirmed_BOR at each visit:

- i) At Visit 1: Use the Visit 1 scan result and refer to [Table 14-2](#) to derive Confirmed_BOR.
- ii) At Visit 2 onward:
 - (a) If current visit is CR: Find last scan that is not NE and at least 28 days before current visit. If current visit is PR: Find last scan that is not NE or SD and at least 28 days before current visit. Derive BOR_temp as below:

Last scan	Current	BOR_temp
CR	CR	CR
PR	CR	PR
PR	PR	PR

- b) If none of above fits, find last scan reference [Table 14-2](#) to derive BOR_temp.

Current visit Confirmed_BOR = best of (BOR_temp, last visit confirmed_BOR). Use rule CR > PR > SD > PD > NE

Step 2. Derive Interim_BOR at last visit prior to DCO	

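### Best overall response is not closed at first progression, so Table 14-3 can turn a subject who has progressed into a confirmed responder or a disease-control success

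*SAP*

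**What the plan says.** **BOR window.** SAP 5.2: "BOR is based on all post-baseline disease assessments that occur prior to the initiation of subsequent anticancer treatment". Protocol 11.10.5 sets the same window. The primary estimand (Protocol 1.1 and 3, SAP 2.1) also names only one stop: "prior to start of new cancer therapy (while-on-treatment strategy").

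**BOR algorithm.** SAP Appendix B ranks the categories: "CR is better than PR is better than SD is better than PD is better than NE". Table 14-3 Step 1 compares the current scan with one earlier scan to get BOR_temp, and then carries the best value forward: "Current visit Confirmed_BOR = best of (BOR_temp, last visit confirmed_BOR").

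**Scans after PD.** Protocol 6.1.7 allows treatment after first radiologic progression under conditions, and adds: "Subjects should continue to perform all protocol-required procedures as noted in the Schedule of Activities". Imaging is named there, and footnote l of Protocol Table 1-2 says the same. Protocol 8.3.2 sends all scheduled images to BICR.

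**Time-to-event endpoints.** PFS, DOR and DoDC (SAP 5.2, Appendix C) take the first PD as the event. SAP 5.2 also says that PD does not need confirmation.

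**The concern.** BOR reads past the first PD while PFS, DOR and DoDC stop there. One subject can therefore be a PFS event at week 6 and a confirmed responder at week 18. Any resulting error in ORR or DCR is upward. The study has a single arm and tests no hypothesis, so the ORR estimate with its interval is the main result, and no control arm would absorb the error. If the rule stays unstated, programmers will have to decide how to treat these subjects after open-label data have been seen.

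**Working it through.** **1. The plan's own figures.** N = 30. Observed ORR above 25% means at least 8 responders; above 30% means at least 10. Exact binomial tails give 87.6% and 64.2% at a true ORR of 0.35, and 95.6% and 82.4% at 0.40. SAP Table 3.2-1 (88%, 64%, 96%, 82%) reproduces and is not in dispute.

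**2. Tables 14-2 and 14-3 Step 1 applied literally.** Scans are six-weekly (Protocol Tables 1-1 and 1-2), taken here at days 43, 85, 127 and 169. Two worked cases:

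- PD-PR-PR. Visit 1 is PD. At visit 2 the look-back scan is PD, no response pair fits, and row C29 gives PD. At visit 3 the look-back scan is the PR at day 85, which is 42 days earlier. The pair PR, PR gives BOR_temp = PR, and the best of PR and PD is PR.
- PD-SD-SD. Visit 2 gives PD by row C29. At visit 3 the last scan is SD at day 85, past day 35, so row C24 gives SD. The best of SD and PD is SD.

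Row C29 therefore protects only the visit directly after the PD.

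| Sequence | As written | Cut at first PD |
|---|---|---|
| PD-PR | PD | PD |
| PD-SD | PD | PD |
| PD-PR-PR | PR | PD |
| PD-CR-CR | CR | PD |
| PD-SD-PR-PR | PR | PD |
| SD-PD-PR-PR | PR | SD |
| PR-PD-PR-PR | PR | SD |
| PD-SD-SD | SD | PD |
| PD-PR-PD | SD | PD |

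A false response needs two post-PD CR/PR scans at least 28 days apart. A false SD needs one post-PD SD or PR scan at day 35 or later and one further visit.

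**3. Durations.** DOR = (first PD date - response start date + 1) x 12/365.25.

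- PD-PR-PR: (43 - 85 + 1) x 12/365.25 = -1.35 months.
- SD-PD-PR-PR: (85 - 127 + 1) x 12/365.25 = -1.35 months.
- PD-SD-PR-PR: (43 - 127 + 1) x 12/365.25 = -2.73 months.
- PR-PD-PR-PR: (85 - 43 + 1) x 12/365.25 = 1.41 months. This is positive, but the subject is still a responder only through post-PD scans.

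DoDC starts at first dose and cannot be negative. PD-SD-SD counts as disease control with a DoDC of (43 - 1 + 1) x 12/365.25 = 1.41 months, the time to the first PD.

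**4. Size.** One subject is 1/30 = 3.3 points. The number of such subjects is an assumption; the documents give none. For a range of 0 to 3, starting from 9 true responders (Clopper-Pearson 95% CI):

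| Added | ORR | 95% CI |
|---|---|---|
| 0 | 9/30 = 30.0% | 14.7-49.4 |
| 1 | 10/30 = 33.3% | 17.3-52.8 |
| 2 | 11/30 = 36.7% | 19.9-56.1 |
| 3 | 12/30 = 40.0% | 22.7-59.4 |

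**5. The separate slip.** For PR-SD-CR, Table 14-3 skips only NE scans when the current scan is CR. The look-back scan is therefore SD, no pair fits, and row C24 gives SD. The Appendix B text lets a CR confirm a PR and allows SD scans in between, which would give PR. A further CR at least 28 days later gives CR anyway, so the slip matters only when no such scan follows.

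**The case against.** **PD looks like the assumed end of assessment.** Protocol 8.3.1 ends routine imaging at BICR-confirmed PD. Step 2 of Table 14-3 lists PD among the reasons why assessment stops. This shows what the authors probably had in mind. But Protocol 6.1.7 and footnote l keep imaging going in subjects treated beyond PD, and Step 2 sets only Interim_BOR. Neither closes Step 1.

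**The minimum SD duration.** Protocol 11.10.5 requires: "At least 5 weeks from the first dose of tarlatamab must elapse without radiological disease progression". A PD at the week-6 scan comes after that point, so the rule does not bar a later SD. For a PD before day 35 the text would bar it, but the table read literally does not: PD at day 28 with SD at days 70 and 112 returns SD.

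**The path is narrow.** This stands. Under Protocol Table 11-5 a new lesion forces PD, so a subject who progressed through new lesions cannot return to PR while they persist. The primary analysis may come at 13 weeks for the last subjects. PD-PR-PR needs scheduled scans at about weeks 6, 12 and 18, so only earlier enrollees could show it by then. The final analysis has no such limit.

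**BICR may stop reading at its own PD.** The Site Imaging Manual might say so, but it is not among the documents. The protocol and SAP do not.

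**Conclusion.** The concern holds: a stated rule gives a wrong value for the primary endpoint in a foreseeable situation, and it conflicts with the PFS, DOR and DoDC rules. It should be corrected before the primary analysis lock. The size is 3.3 points of ORR or DCR per affected subject, upward; the number affected is unknown and may be zero.

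Exposure differs by assessor. BICR ORR and DCR are affected only when treatment continues after a BICR PD. If the investigator calls PD and BICR does not, continuing the BICR BOR is correct; in that case only the investigator-assessed secondary endpoints are affected.

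A reader might infer more than the documents support:

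- *That responses are read against a reset baseline.* Protocol 6.1.7 does mention "progressive disease per RECIST 1.1 from a new baseline set at initial progression", but as a stopping rule based on the investigator's assessment. Protocol 11.10.3.1.1 and Table 11-3 measure response from the original baseline.
- *That any single response or SD after PD counts.* PD-PR and PD-SD with no later scan stay PD.
- *That DOR fails in general.* It is negative only when the first response follows the first PD.
- *That a total inflation can be stated.* That needs a count of subjects treated beyond PD with qualifying scans, which the documents do not give. No hypothesis is tested, so no decision limit is crossed either.

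**What to change.** 1. In SAP 5.2, SAP Appendix B and Protocol 11.10.5, state that BOR uses assessments through the first PD by the same assessor (BICR or investigator), or before subsequent anticancer therapy, whichever is earlier.
2. Put the same limit in the estimand wording (Protocol 1.1 and 3, SAP 2.1). Otherwise the estimand and the BOR rule will no longer match.
3. In Table 14-3 Step 1, process the visit with the first PD and then freeze Confirmed_BOR.
4. As a separate correction in Table 14-3, add for a current CR: if the last scan that is neither NE nor SD, and is at least 28 days earlier, is PR, then BOR_temp = PR.

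The cost is SAP and protocol wording and a small program change; no new data are needed. Items 1 to 3 may make ORR and DCR slightly less favourable. Item 4 can move an occasional subject from SD to PR.

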8.4.4 Vital Status (Survival Status)

Vital status (survival status) must be obtained for all subjects within the limits of local law. This includes subjects who may have discontinued study visits with or without withdrawing consent and should include interrogation of public databases, if necessary and legally permissible. If deceased, the date and reported cause of death should be obtained.

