3.1 Study Design

This is a phase 2a, multicenter, single arm, open-label study in Chinese subjects with advanced SCLC who have progressed on or recurred following 1 platinum-based regimen as 1L therapy (including a PD-1/PD-[L]1) and at least 1 other prior line of therapy (re-treatment with a platinum-based regimen is considered a second line of therapy). The study consists of a 21-day screening period, a treatment period, a safety follow-up (SFU) period, and a long-term follow-up (LTFU) period.

A SFU visit will occur 60 (+ 5) days after the last dose of tarlatamab regardless of initiation of subsequent anticancer therapy within that period. After the SFU visit,

subjects will be followed in LTFU for survival every 12 weeks (+/-14 days) for up to 1 year after the **last** subject's last dose of tarlatamab or 5 years from the first subject enrolled, whichever occurs first.

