5.1 General Definitions

Baseline

For any variable, unless otherwise specified, baseline is the last non-missing assessment taken prior to the first administration of tarlatamab. Where baseline measurements are taken on the same day as the tarlatamab administration and no time is present, it is assumed that these measurements are taken prior to tarlatamab administration.

Change from Baseline

Change from baseline = post-baseline value – baseline value.

Percent Change from Baseline

Percent change from baseline = $100 * (\text{post-baseline value} - \text{baseline value}) / \text{baseline Value}$

Body Mass Index (BMI)

$\text{BMI (kg/m}^2\text{)} = \text{weight (kg)} / [\text{height (cm)} / 100]^2$

Investigational Product (IP)

Investigational product refers to tarlatamab.

Study Day

Study day = (date - date of study day 1) + x; where

x = 1 if date is after study day 1;

x = 0 if date is before study day 1.

Study Day 1

Study day 1 is defined as the date of the first dose of tarlatamab administration to the Subject.

Treatment Duration

Treatment duration (weeks) = (last dose date – first dose date + 1) / 7.

Relative Dose Intensity

Relative dose intensity (%) = $100 * (\text{Actual cumulative dose} / \text{Planned cumulative dose})$;

Actual cumulative dose = sum of received doses.

Planned cumulative dose = planned dose accumulated over the actual treatment duration,

i.e., $10 \text{ mg} \times (\text{number of records in exposure dataset} - 1) + 1 \text{ mg}$; 1 mg is the step dose on C1D1.

Actual and planned cumulative dose up to the study visit are considered.

Last Known Alive Date

Last known alive date is the latest date of the following dates before death date. Other Case Report Form (CRF) data may be explored to get the last known alive date. Last known alive date should be imputed the first day of the month for the partial date when the month and year are available, but day is missing.

- Date of consent signed, and date of consent withdrawn from additional consents/withdrawals of consent form
- Date of Enrollment date on Subject Enrollment CRF
- Date First Taken, Date Last Taken on Concomitant Medications CRF
- Date Performed on MUGA/ECOG Performance Status, Vital Signs, Echocardiogram, Electrocardiogram, Surgical Procedures, Procedure CRFs
- Admission Date, Discharge Date on Hospitalizations CRF, Date of Examination on Physical Measurement CRF

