- Date Collected on Reproductive Status and Pregnancy Test (Local Lab), Chemistry (Local Lab), Hematology (Local Lab), Coagulation (Local Lab) CRFs, Urinalysis (Local Lab) and in central lab data
- Start Date, Stop Date on Product Administration CRF
- Start Date, Stop Date on Other Protocol Required Therapy CRF
- Date Started and Date Ended on Events CRF for non-fatal events
- Tumor response and NYHA Classification date
- Target/non-target assessment date
- CRS Symptoms and ICANS date

- End of study, end of safety follow-up and end of administration date where end reason is not death or lost to follow-up
- Start date, Stop date on On-Study Radiotherapy, Anti-Cancer Therapies (Subsequent) CRF
- Subject Status Date if status is Alive on Survival Status CRF
- Assessment Date of CT or MRI
- Date of Liver biopsy
- Neurological Evaluation date
- Date of Clinical Outcome Assessments
- If death happened, then last known alive date is death date minus 1.
- Date of Anti-body sample
- Date of PK sample
- Date/Time of Tumor Measurement
- Date/Time of Tumor Identification
- Date/Time of Response Assessment

End of IP Administration

End of IP administration for each subject is defined as the date the decision was made to end IP as recorded on the End of Product Administration eCRF page.

End of Study Date (End of Trial)

The end of study date for the entire study is defined as the date when the last subject across all sites is assessed or receives an intervention for evaluation in the study (ie, last subject last visit) including any additional parts in the study (eg, LTFU, antibody testing), as applicable.

End of Study (Individual Subject)

End of study for each subject is defined as the date the subject last completed a protocol specified procedure. The date will be recorded on the End of Study eCRF page.

Safety Follow-up (SFU)

Upon permanent discontinuation from the study treatment for any reason, a safety follow up visit will be performed approximately 60 (+ 5) days after the end of the last dose of tarlatamab, regardless of initiation of subsequent anticancer therapy within that period.

Long Term Follow-up (LTFU)

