Following the SFU visit (60 [+ 5] days), subjects will enter the LTFU period for clinical evaluation of disease status and survival. Subjects will be followed via telephone, clinic visit, or chart review to assess for survival and/or the commencement of subsequent cancer therapy every 12 weeks (\pm 14 days) from the SFU visit or last imaging visit, whichever is later, for up to 1 year after the last subject's last dose of tarlatamab or 5 years from first subject enrolled, whichever occurs first.

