9.5.2 Analyses of Secondary Efficacy Endpoint(s)/Estimand(s)

Table 9-2. Example Secondary Efficacy Endpoint/Estimand Summary Table

Endpoint/Estimand	Primary Summary and Analysis Method	Sensitivity Analysis
DCR based on BICR	Proportion of subjects with DC, corresponding Clopper-Pearson (Clopper and Pearson, 1934) exact 95% CI.	Repeat summary on RECIST 1.1 evaluable by blinded independent central reviewer analysis set.
DoDC, DOR, PFS based on BICR	Distribution of DoDC, DOR, PFS, corresponding median and percentiles using Kaplan-Meier (KM) method with 95% CI calculated using the Brookmeyer and Crowley (Brookmeyer and Crowley, 1982) method.	Repeat summary on RECIST 1.1 evaluable by blinded independent central reviewer analysis set.
ORR, DCR based on investigator assessment	Proportion of subjects with OR, DC, corresponding Clopper-Pearson (Clopper and Pearson, 1934) exact 95% CI.	None
DoDC, DOR, PFS based on investigator assessment	Distribution of DoDC, DOR, PFS, corresponding median and percentiles using Kaplan-Meier (KM) method with 95% CI calculated using the Brookmeyer and Crowley (Brookmeyer and Crowley, 1982) method.	None

Endpoint/Estimand	Primary Summary and Analysis Method	Sensitivity Analysis
OS	Distribution of OS, corresponding median and percentiles using Kaplan-Meier (KM) method with 95% CI calculated using the Brookmeyer and Crowley (Brookmeyer and Crowley, 1982) method.	None

The efficacy analyses of secondary endpoints will be conducted on the safety analysis set, unless otherwise specified.

For ORR based on investigator assessment, the proportion of subjects with PR or better and corresponding Clopper-Pearson 95% CI will be presented. For DCR based on BICR and DCR based on investigator assessment, the proportion of subjects with DC and corresponding Clopper-Pearson 95% CI will be presented.

The distribution of DoDC, DOR, and PFS (per RESIST 1.1 based on BICR) and the distribution of OS, including median and percentiles using Kaplan-Meier (KM) method with 95% CI calculated using the Brookmeyer and Crowley will be presented. Landmarks at selected time points (e.g. 3, 6, 9 and 12 months) with 95% CI calculated using the Greenwood formula (Kalbfleisch and Prentice, 1980) to estimate the standard error in CI calculation will be provided. For DoDC, percentages of subjects with DoDC ≥ 4 months will also be provided.

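### At the primary analysis, OS censors living long-term follow-up subjects at a contact that may be weeks old but counts deaths whenever known, so late landmarks can shift by a few points with reporting speed

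*SAP*

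**What the plan says.** **Censoring rule.** SAP 5.2: "Subjects still alive are censored at the date last known to be alive". One adjustment follows: if that date is later than the cut-off, "the subject is censored at the data cut-off date". A date earlier than the cut-off is left where it is.

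**Where the date comes from.** SAP 5.1: "Last known alive date is the latest date of the following dates before death date". The list of sources is long (visits, laboratory samples, imaging, hospitalisation, later anticancer therapy, the Survival Status CRF), but no maximum age is set. For a subject who has died: "If death happened, then last known alive date is death date minus 1".

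**How often contact is made.** On treatment, dosing visits fall every 2 weeks. A safety visit follows 60 to 65 days after the last dose. After that, SAP 5.1 and Protocol 8.1.5 provide for contact by telephone, clinic visit or chart review "to assess for survival and/or the commencement of subsequent cancer therapy every 12 weeks", with a 14-day window either way.

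**Vital status.** Protocol 8.4.4: "Vital status (survival status) must be obtained for all subjects within the limits of local law". Public databases may be used where lawful. No timing relative to a data cut-off is given.

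**Death reporting.** Under Protocol 8.4.6.1.2, a death from progression goes on the End of Study CRF and is not a serious adverse event unless a causal link to treatment is suspected. The 24-hour reporting clock therefore does not normally apply to it.

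**When OS is analysed.** SAP Section 1 covers both the primary and the final analysis, and OS is not held back for the final one. SAP 7.2 requires at most 13 weeks of follow-up of the last subject. SAP 9.5.2 plans Kaplan-Meier landmarks, giving 3, 6, 9 and 12 months as examples.

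**The concern.** Kaplan-Meier estimation assumes that a subject censored at a given time has the same prospects as those still under observation. At the primary cut-off that assumption is strained in one of two ways.

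- If deaths reach the database promptly, a death since the last contact counts as an event, but survival through the same interval earns no time at risk. The estimate is then too low.
- If deaths are learned only at scheduled contacts, subjects off treatment, who are mostly past progression and at the highest risk, leave the risk set early and their recent deaths are missing. The estimate is then too high.

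The plan does not determine which of these applies; site reporting habits do. At stake is how OS is described at the primary analysis, especially at the latest landmark, where few subjects remain at risk. The reported confidence interval does not cover this error.

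**Working it through.** The documents give no OS precision figure to reproduce. The design figures in SAP Table 3.2-1 concern response and adverse events; they reproduce and are not at issue here.

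**1. Age of the last contact.** 84 + 14 = 98 days, or 14 weeks, after an on-schedule contact. If one contact is early and the next late, 84 + 28 = 112 days. A 98-day gap after a safety visit at day 60 needs 60 + 98 = 158 days of follow-up. With the cut-off 91 days after the last enrolment, only subjects enrolled at least 158 - 91 = 67 days before the last one can reach it.

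In simulation the mean lag was about 5 weeks among the roughly 11 subjects alive and off treatment. Among all living subjects the median was 9 to 12 days, 6% to 22% exceeded 6 weeks, and under 2% exceeded 12 weeks.

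**2. Survival model.** Inputs from Protocol 2.3 are a median PFS of 4.9 months and a 9-month OS of 68%. Assumptions not in the documents are uniform accrual, exponential hazards, and f = 12% of PFS events being deaths.

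- Progression hazard: h = ln 2 / 4.9 = 0.1415 per month.
- Post-progression hazard g solves S(9) = exp(-9h) + (1 - f) h [exp(-9g) - exp(-9h)] / (h - g) = 0.68.
- g is about 0.0894 per month. Check: 0.280 + 0.1245 x (0.4473 - 0.2800) / 0.0521 = 0.280 + 0.400 = 0.680.

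Contacts are every 14 days on treatment, at progression, at 60 to 65 days after the last dose, then every 84 days (±14). The cut-off is 91 days after the last enrolment.

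**3. Results, 9-month accrual (400,000 simulated subjects).** Kaplan-Meier estimate, with bias in points in brackets:

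| When deaths become known | 6-month OS | 9-month OS |
|---|---|---|
| True value | 80.3% | 67.9% |
| At once | 79.2% (-1.1) | 64.4% (-3.5) |
| After 14 days | 79.9% (-0.4) | 66.5% (-1.4) |
| After 28 days | 80.8% (+0.5) | 68.6% (+0.7) |
| Only at next contact | 81.1% (+0.8) | 69.9% (+2.0) |
| Status confirmed for all at cut-off | 80.3% (0) | 67.9% (0) |

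Runs with small differences in the contact model gave +2.8 to +3.3 points for contact-only reporting, -0.7 with half of deaths reported promptly, and -1.7 and +0.1 for the 14- and 28-day lags. With 6-month accrual, 6-month OS is 78.2% (deaths known at once) or 81.8% (contact only) against 80.3%, a shift of -2.1 or +1.5.

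**4. Worse survival.** Protocol 2.2.1 cites a median OS of 6.86 months for a comparator treatment. If exponential, 9-month OS is 2^(-9/6.86) = 40%. With 9-month accrual the 9-month estimate is then 37.4% (at once), 39.8% (14 days), 42.5% (28 days) or 44.6% (contact only), against 40.0%.

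**5. Scale.** The binomial standard error at 68% with 30 subjects and no censoring is sqrt(0.68 x 0.32 / 30) = 8.5 points. With 9-month accrual only about 30 x (3/9) x 0.68 = 7 subjects are at risk at 9 months, and the simulated standard deviation of the estimate is about 11 points.

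**The case against.** The strongest reply is that the extremes are unlikely and the setting is forgiving. Real reporting lies between immediate and contact-only, where the two effects largely cancel. The bias is below the sampling error. OS is secondary, nothing is tested, and the final analysis follows completed long-term follow-up. All of this stands.

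The simulated lag is also probably on the long side. It leaves out treatment beyond progression (Protocol 6.1.7), continued imaging in subjects who stop without centrally confirmed progression (Protocol 8.3.1), and other dates that feed the last-known-alive date, such as hospitalisation and later therapy. That stands too, though none of these guarantees a recent date for a subject who is off treatment and past progression.

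It can further be said that Protocol 8.4.4 already requires vital status and SAP 7.2 expects data issues to be settled before lock. This stands only in part. The duty has no date, and a long-term follow-up subject last seen 8 weeks ago is on schedule, so no data query would arise.

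That deaths count whenever they are learned is itself an inference: no rule restricts events to those found at a scheduled contact, but the SAP does not say so in terms.

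**Conclusion.** The point holds as a modest, avoidable bias in OS at the primary analysis. Under the assumed 9-month accrual and the global study's survival, 9-month OS shifts by about -3.5 to +3 points at the extremes of reporting and by 0 to 2 points in between. Six-month OS shifts by about 1 to 2 points at the extremes. If survival is nearer the 40% scenario, the 9-month range is -2.6 to +4.6 points, with +2.5 for a 28-day lag. Accrual duration, the hazards and reporting speed are assumptions.

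Three stronger readings are tempting, and the documents do not support them.

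- A reader might infer that OS at the primary analysis cannot be interpreted or set beside the global study. The bias is smaller than the sampling error, and the documents plan no formal comparison.
- A reader might take 14 weeks as the usual lag. It is close to a worst case.
- A reader might look for a 9-month figure under 6-month accrual. Six months plus 91 days is just under 9 months, so no subject has that much follow-up and the landmark is not estimable.

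**What to change.** Add one sentence to SAP 7.2 and to the data-cut instructions. For every subject not known to be dead, obtain survival status by telephone, chart review or permitted public records on or within about 14 days after the data cut-off, and enter it on the Survival Status CRF. Count only deaths on or before the cut-off as OS events. Censor subjects confirmed alive on or after the cut-off at the cut-off date, which extends the cap already in SAP 5.2.

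The cost is one extra status check for roughly a dozen subjects, since those on treatment are seen every 2 weeks anyway. No protocol amendment is needed, because Protocol 8.1.5 and 8.4.4 already permit these contacts. The same sentence can go into 8.1.5 when the protocol is next amended.
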